## SYNOPSIS

Protocol Title	Evaluation of the JJVC Investigational Toric Multifocal Contact Lens Fitting Guide Phase II
Sponsor	JJVC, [name]
Clinical Phase	Phase 2
Trial Registration	This study will be registered on ClinicalTrials.gov by the Sponsor
Test Article(s)	Investigational Products: etafilcon A Toric Multifocal Contact Lens Marketed Products: 1-Day Acuvue® Moist Brand Multifocal Contact Lens
Wear and Replacement Schedules	Wear Schedule: Daily Wear Replacement Schedule: None- Non-dispensing study
Objectives	The primary objective of this study is an evaluation of the JJVC Investigational Toric Multifocal and 1-Day Acuvue® Moist Brand Multifocal Contact Lens fitting guides by Eye Care Providers (ECPs).

[REDACTED] (5)

Study Endpoints	
Primary endpoint: The maximum number of lens modifications for both eyes required by the ECP to optimize the lenses for vision.
 
Secondary endpoint:
 
 
1. Subjective feedback from the ECP on the fitting guide process (i.e. intuitive nature of the fitting steps, adequate amount of information provided by the fitting guide, strengths and weaknesses, etc.)
 
2. Subjective feedback from the ECP regarding the layout of the fitting guide.
 
3. Surveys of the subjects experience.
 

Study Design	
This study is a single arm, non-randomized, open label, non-dispensing clinical trial. The key assessments for this study will be the number of fitting modifications and ECP feedback throughout the fit process while using the Fit Guide. Each ECP will fit at least 3 subjects and no more than 4.
 
See the flow chart at the end of the synopsis table for the schematic of the study visits and procedures of main observations.

Sample Size	
A total of approximately 32 subjects will be enrolled into the study. Approximately 24 are targeted to complete.

Study Duration	
The study duration is anticipated to be approximately 1 week.

Anticipated Study Population	
Healthy male and female volunteers with presbyopia will be screened as per criteria outlined below.

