	
11. Use of any ocular medication, with the exception of rewetting drops.
 
12. History of herpetic keratitis.
 
13. Participation in any contact lens or lens care product clinical trial within 30 days prior to study enrollment.
 
14. Employee of clinical site (e.g., Investigator, Coordinator, Technician)

Disallowed Medications/Interventions	Any systemic medications that may affect contact lens wear and any ocular medications with the exception of rewetting drops.
Measurements and Procedures	The key assessments for this study will be the number of fitting modifications and ECP feedback throughout the fit process while using the Fit Guide.
Microbiology or Other Laboratory Testing	None
Study Termination	The occurrence of one or more Unanticipated Adverse Device Effect (UADE), or any SAE where relationship to study agent cannot be ruled out, will result in stopping further dispensing investigational product. In the event of a UADE or SAE, the Sponsor Medical Monitor may unmask the treatment regimen of subject(s) and may discuss this with the Principal Investigator before any further subjects are enrolled.
Ancillary Supplies/ Study-Specific Materials	Eye-Cept® rewetting drops
Principal Investigator(s) and Study Institution(s)/Site(s)	A full list of Principal Investigators, clinical sites, and institutions is kept separately from the Study Protocol and is included in the study Trial Master File.

████████ (5)

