## **11. STUDY TERMINATION**

If more than 2 subjects in the investigational soft contact lens group develop serious expected (e.g., definite or probable MK) or unexpected device related adverse events, the study will be suspended. Upon review and consultation with IRB, and JJVC safety review committee, the study may be terminated.

The occurrence of one or more Unanticipated Serious Adverse Device Effect (USADE), or any SAE where the relationship to study agent cannot be ruled out, may result in stopping further dispensing of Test article. In the event of a USADE or SAE, the Sponsor may unmask the treatment regimen for the subject(s) and will discuss this with the Investigator before any further subjects are enrolled.

The Sponsor will determine when a study will be stopped. The Principal Investigator always has the discretion to initiate stopping the study based on patient safety or if information indicates the study's results are compromised.

JJVC reserves the right to terminate the study at any time for any reason. Additionally, the IEC/IRB reserves the right to terminate the study if an unreasonable risk is determined. The study can be terminated by the Principal Investigator at the individual clinical site due to specific clinical observations, if in their opinion, after a discussion with JJVC, it is determined that it would be unwise to continue at the clinical site.

JJVC (and the IEC/IRB and DMC, if applicable) will evaluate all adverse events. If it is determined that an adverse event presents an unreasonable risk, the investigation, or that part of the investigation presenting the risk, will be terminated, as soon as possible.

[REDACTED] (5)

Should the study be terminated (either prematurely or as scheduled), the Investigator will notify the IEC/IRB and Regulatory Authority as required by local regulatory requirements.

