- Central Corneal Neovascularization
- Uveitis
- Endophthalmitis
- Hypopyon
- Hyphemia
- Penetration of Bowman's Membrane
- Persistent Epithelial Defect
- Limbal cell Damage leading to Conjunctivalization

**Significant Adverse Events** – Those events that are usually symptomatic and warrant discontinuation (temporary or permanent) of the Test article (excluding Serious Adverse Events).

Diagnoses and conditions that are considered Ocular Significant Adverse Events include, but not limited to the following:

- Contact Lens Induced Peripheral Ulcer (CLPU)
- Significant Infiltrative Events (SIE)
- Superior Epithelial Arcuate Lesions (SEALs)
- Any Temporary Loss of > 2 Lines of BSCVA
- Other Grade 3 or higher corneal findings, such as abrasions or edema

- Non-contact lens related corneal events - e.g. Epidemic Keratoconjunctivitis (EKC)
- Asymptomatic Corneal Scar
- Any corneal event which necessitates temporary lens discontinuation > 2 weeks

**Non-Significant Adverse Events** – Those conditions that are usually asymptomatic and usually do not warrant discontinuation (temporary or permanent) of the Test article. However, the Investigator may choose to treat as a precautionary measure.

Diagnoses and conditions that are considered Ocular Non-Significant Adverse Events include, but not limited to the following:

- Non-significant Infiltrative Event (NSIE)
- Contact Lens Papillary Conjunctivitis (CLPC)
- Superficial Punctate Keratitis (SPK)
- Conjunctivitis: Bacterial, Viral, Allergic
- Blepharitis
- Meibomianitis
- Contact Dermatitis
- Localized Allergic Reactions
- Any corneal event not explicitly defined as serious or significant adverse event, which necessitates temporary lens discontinuation < 2 weeks

**Adverse Device Effect (ADE)** – A sub-set of AEs, and include only those adverse events that are cause by or related to the investigational device.

**Unanticipated Adverse Device Effect (UADE)** – Any serious adverse effect on health or safety or any life-threatening problem or death caused by, or associated with, the Test article, if that effect, problem, or death was not previously identified in nature, severity, or degree of incidence in the investigational plan, Investigator's Brochure or protocol, or any other unanticipated serious problem associated with the Test article that relates to the rights, safety and welfare of subjects.

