### **Unanticipated (Serious) Adverse Device Effect (UADE)**

In the event of an Unanticipated (Serious) Adverse Device Effect (UADE), the Investigator will submit a report of the UADE to the Sponsor and IEC/IRB as soon as possible, but no later than 24 hours after the Investigator first learns of the effect. This report is in addition to the immediate notification mentioned above.

The Sponsor must conduct an evaluation of the UADE and must report the results of the evaluation to FDA, the IEC/IRB and participating Investigators within 10 working days after the Sponsor first receives notification of the effect.

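### After a first serious device-related event the Synopsis requires lens dispensing to stop, Section 11 only permits it, and nothing says which governs

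*Combined protocol and SAP*

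**What the plan says.** The Study Termination row of the Synopsis says that one or more UADEs, or an SAE whose relationship to the study agent cannot be excluded, "will result in stopping further dispensing investigational product". It adds that the Sponsor Medical Monitor "may discuss this with the Principal Investigator before any further subjects are enrolled".

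Section 11 (Study Termination) gives the same SAE condition and uses the label USADE in place of UADE. It says the event "may result in stopping further dispensing of Test article", and that the Sponsor "will discuss this with the Investigator before any further subjects are enrolled".

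Section 13.1 defines UADE but not USADE, which appears in the abbreviation list and in Section 11. The definition begins "Any serious adverse effect on health or safety or any life-threatening problem or death".

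Section 11 also contains a separate rule that suspends the study once more than 2 subjects in the investigational lens group have serious expected or unexpected device-related events. It provides for termination if an adverse event is judged an unreasonable risk, and it leaves the Sponsor and the Principal Investigator discretion to stop.

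**The concern.** A first-event stopping rule has to tell the site what to do on the day of the event. Here the site has two instructions. Under the Synopsis, dispensing of the investigational lens stops. Under Section 11, dispensing may continue provided the Sponsor talks to the Investigator before anyone else is enrolled. A site that continued fitting after that discussion would comply with Section 11 and breach the Synopsis.

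What is at stake is whether further subjects have an investigational lens inserted before anyone has decided that this is acceptable. Section 11's discussion step is tied to enrolment. It does not by its terms cover a subject who is already enrolled and waiting for a first or a modified lens.

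**Working it through.** No arithmetic applies. The check sets the two texts side by side and asks whether any difference in wording removes the conflict.

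| Element | Synopsis, Study Termination | Section 11 |
|---|---|---|
| Device-effect trigger | One or more UADE | One or more USADE |
| SAE trigger | Any SAE whose relationship to the study agent cannot be excluded | Same |
| Effect on dispensing | Mandatory (*will*) | Optional (*may*) |
| What is stopped | Investigational product | Test article |
| Discussion before further enrolment | Optional (*may*), Medical Monitor with Principal Investigator | Mandatory (*will*), Sponsor with Investigator |
| Length of stop, rule for resuming | Not stated | Not stated |

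**Do the labels separate the triggers?** No. The UADE definition in Section 13.1 is already confined to serious effects, life-threatening problems, death and other serious problems. Section 13.4.1 puts the word Serious in brackets inside the same term: "In the event of an Unanticipated (Serious) Adverse Device Effect (UADE"). The SAE trigger is in any case the same in both texts, and it is enough by itself to produce the conflict.

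**Do the objects separate the rules?** Only in part. Section 1.1 names the toric multifocal as the investigational product and the 1-Day Acuvue Moist Multifocal as marketed. Table 1 in Section 6.1 lists both as test articles. Read literally, the Synopsis stop covers the toric lens only, while Section 11's optional stop covers both. For the toric lens, *will* and *may* still collide. For the marketed lens, only the optional rule exists.

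**Does dispensing mean anything in a non-dispensing study?** Yes, on the protocol's own usage. Section 6.7 counts lenses given for trial fitting among those dispensed.

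**Does any text give precedence?** No. The Change History does not mention this wording, and no section ranks the Synopsis against the body. Section 11 says the Sponsor determines when a study is stopped. That concerns stopping the study and does not address the Synopsis's stop on dispensing.

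**Which actions satisfy both texts?**
- Stop, discuss, then decide: satisfies both.
- Discuss and continue fitting the toric lens: satisfies Section 11, breaches the Synopsis.
- Stop, then resume enrolment without discussion: allowed by the Synopsis, which sets no condition for resuming, but breaches Section 11.

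A compliant path therefore exists, but the protocol does not direct the site to it.

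**The case against.** The strongest reply is that this is a mismatch between a summary row and the body, with little riding on it. Each subject attends one supervised visit (Section 4.1), and exit biomicroscopy is scheduled within it (Section 7.2, step 1.26). Serious and significant events reach the Sponsor within 24 hours (Section 13.4). Section 11's discussion step and its other stopping routes remain available. All of this stands, and it limits the weight of the point. It does not settle what must happen at the first event: the more-than-2-subjects rule is a separate tier, unreasonable-risk termination needs a prior determination, and the remaining routes are discretionary. A summary may leave out detail, but this one imposes a stricter duty than the text it summarises.

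It is also fair to say that either wording could have been chosen. The defect is that both are in force.

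Two stronger readings are tempting, and the documents support neither.

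- A reader might count every subject not yet fitted as depending on the wording: up to 32 - 1 = 31 of the 32 enrolled if the first subject is affected. That treats the Synopsis stop as permanent. The Synopsis gives no duration, and its next sentence contemplates further enrolment. It also reaches only the investigational product, and Section 4.3 promises only an attempt to recruit subjects with enough cylinder to need the toric lens, so some subjects might wear marketed lenses only.
- A reader might compare the Sponsor's deadline for reporting its UADE evaluation, "within 10 working days after the Sponsor first receives notification of the effect", with the planned length, "The study duration is anticipated to be approximately 1 week", and infer that the study would finish without a safety decision. The deadline is an outer limit for reporting. It is not the time needed to decide on a pause, and a sensible rule would not make resumption wait for that report.

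**Conclusion.** The conflict holds on the text. For the investigational lens, one current rule requires a stop after a first qualifying event and the other leaves it to discretion. The discussion duty runs the opposite way, and nothing says which prevails. Whether fitting must pause is therefore undefined.

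The size is modest. The inconsistency bears on subject protection and site compliance, not on any statistical quantity. It would be wrong to infer uncontrolled exposure. The documents give no event rate, so no probability is attached.

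The conclusion rests on three readings: that UADE and USADE mean the same thing, that dispensing includes in-office trial fitting, and that the matter to be discussed before further enrolment is the event itself. The last is the natural reading because the alternative, unmasking, cannot arise in an open-label study without randomization (Sections 5.2 and 5.3). The first is not essential, because the shared SAE trigger carries the point.

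**What to change.** Put one rule in both the Synopsis and Section 11. Any UADE, or any SAE whose relationship to the study agent cannot be excluded, pauses enrolment and further insertion of the investigational toric multifocal lens. The pause lasts until the Sponsor and Investigator have discussed the event and documented a decision to resume.

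In the same edit:
- Use UADE, the term Section 13.1 defines, in both places and drop USADE.
- State whether the pause also covers the marketed multifocal lens. The Synopsis wording does not reach it, so including it would extend the mandatory stop and should be a deliberate choice.
- Keep the more-than-2-subjects suspension as a separate tier.
- Delete the unmasking wording, but keep the duty to discuss that now shares its sentence.

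This is a protocol wording amendment. Sample size, visits and analysis do not change. The downside is a possible short pause in a study of about one week.

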## **12. PROCEDURE FOR HANDLING PRODUCT QUALITY COMPLAINTS**

A Product Quality Complaint (PQC) refers to any written, electronic, or oral communication that alleges deficiencies related to the identity, quality, durability, reliability, safety, effectiveness or performance of Test articles after they have been released for clinical trial use.

Potential complaints may come from a variety of sources including but not limited to subjects, clinical research associates (CRA), clinical operations managers (COM), medical monitors, and site personnel, etc. The following are not considered product quality complaints:

- Subject satisfaction inquiries reported via “Subjective Questionnaires” and “Patient Reported Outcomes (PRO)”.
- Clinical Test articles that are stored improperly or damaged after receipt at the investigational site.
- Lens replacements that occur due to drops/fall-outs.
- Damage deemed by clinicians or clinical staff to be caused by handling by the user, and not indicative of a quality deficiency (i.e. tears, rips, etc.), only in situations where there is no deficiency alleged by the subject.

Within 24 hours of site personnel becoming aware that a PQC has occurred, the PQC must be recorded in the EDC system, which will trigger an automatic email notification to the appropriate COM/CRA and Clinical QA representative. In cases where the EDC system in use is not configured to send automatic notifications or when an EDC system is not used, the COM/CRA is responsible for notifying Clinical QA upon discovery that a PQC has occurred.

Upon receipt of the EDC notification, the COM/CRA will contact the study site to collect additional information which will include:

- Date the complaint was received/recorded in the EDC System (Date of Sponsor Awareness)
- Who received the complaint
- Study number
- Clinical site information (contact name, site ID, telephone number)
- Lot number(s)
- Unique Subject Identifier(s)
- Indication of who first observed complaint (site personnel or subject)
- OD/OS indication, along with whether or not the lens was inserted
- Any related AE number if applicable

████████ (5)

- Detailed complaint description (scheduled/unscheduled visit, wear time, symptoms, resolution of symptoms, etc.)
- Eye Care Provider objective (slit lamp) findings if applicable
- Confirmation of product availability for return (and tracking information, if available), or rationale if product is not available for return (Refer to [REDACTED] for Test article return instructions)

Once a complaint is received, it will be assessed by the COM, CRA, or trained site personnel to determine if it is an Adverse Event/Serious Adverse Event (AE/SAE). If the complaint results in an AE/SAE, the COM/CRA, or trained site personnel will follow Section 13 of this protocol. If the AE/SAE was potentially the result of a product quality related deficiency, these procedures also applies and will be executed in parallel.

In some cases, a PQC form may be generated in EDC by the site in error. In this event, the PQC forms will be marked “Intentionally Left Blank” or “ILB”. Justification for ILB must be documented.

### 13. ADVERSE EVENTS

#### 13.1. Definitions and Classifications

**Adverse Event (AE)** – An AE is any untoward (unwanted) medical occurrence in a patient or clinical investigation subject administered a Test article, study treatment or study procedure whether or not caused by the Test article, study treatment or procedure. An AE can therefore be any unfavorable or unintended sign (including an abnormal finding), symptom, or disease temporally associated with the use of the Test article, study treatment, or study procedure whether or not related to the Test article, study treatment, or study procedure.

An AE includes any condition (including a pre-existing condition) that:

1. Was not present prior to the study, but appeared or reappeared following initiation of the study
2. Was present prior to the study, but worsened during the study. This would include any condition resulting from concomitant illnesses, reactions to concomitant medications, or progression of disease states
3. Pregnancy must be documented as an adverse event and must be reported to the clinical monitor and to the Sponsor immediately upon learning of the event

**Serious Adverse Event (SAE)** – An SAE is any untoward medical occurrence that:

- Results in death
- Is life threatening

[REDACTED] (5)

- Requires in-patient hospitalization or prolongation of existing hospitalization
- Results in persistent or significant disability/incapacity (e.g., a sight threatening event, a significant persistent or permanent change, impairment, damage, or disruption to the subject's body)
- Is a congenital anomaly/birth defect, or
- Requires intervention to prevent permanent damage (the use of the Test article resulting in a condition which requires medical or surgical intervention to preclude permanent impairment of the body structure or a body function). Important medical events that may not result in death, be life-threatening, or require hospitalization may be considered an SAE when, based upon appropriate medical judgment, they may jeopardize the patient or subject and may require medical or surgical intervention to prevent one of the outcomes listed in the above definition.

Diagnoses and conditions that are considered Ocular Serious Adverse Events include, but not limited to:

- Microbial Keratitis (MK)
- Iritis (including cells in the anterior chamber)
- Permanent decrease in best spectacle corrected visual acuity equivalent to 2 acuity lines or greater
- Central Corneal Opacity
- Central Corneal Neovascularization
- Uveitis
- Endophthalmitis
- Hypopyon
- Hyphemia
- Penetration of Bowman's Membrane
- Persistent Epithelial Defect
- Limbal cell Damage leading to Conjunctivalization

**Significant Adverse Events** – Those events that are usually symptomatic and warrant discontinuation (temporary or permanent) of the Test article (excluding Serious Adverse Events).

Diagnoses and conditions that are considered Ocular Significant Adverse Events include, but not limited to the following:

- Contact Lens Induced Peripheral Ulcer (CLPU)
- Significant Infiltrative Events (SIE)
- Superior Epithelial Arcuate Lesions (SEALs)
- Any Temporary Loss of > 2 Lines of BSCVA
- Other Grade 3 or higher corneal findings, such as abrasions or edema

- Non-contact lens related corneal events - e.g. Epidemic Keratoconjunctivitis (EKC)
- Asymptomatic Corneal Scar
- Any corneal event which necessitates temporary lens discontinuation > 2 weeks

**Non-Significant Adverse Events** – Those conditions that are usually asymptomatic and usually do not warrant discontinuation (temporary or permanent) of the Test article. However, the Investigator may choose to treat as a precautionary measure.

Diagnoses and conditions that are considered Ocular Non-Significant Adverse Events include, but not limited to the following:

- Non-significant Infiltrative Event (NSIE)
- Contact Lens Papillary Conjunctivitis (CLPC)
- Superficial Punctate Keratitis (SPK)
- Conjunctivitis: Bacterial, Viral, Allergic
- Blepharitis
- Meibomianitis
- Contact Dermatitis
- Localized Allergic Reactions
- Any corneal event not explicitly defined as serious or significant adverse event, which necessitates temporary lens discontinuation < 2 weeks

**Adverse Device Effect (ADE)** – A sub-set of AEs, and include only those adverse events that are cause by or related to the investigational device.

**Unanticipated Adverse Device Effect (UADE)** – Any serious adverse effect on health or safety or any life-threatening problem or death caused by, or associated with, the Test article, if that effect, problem, or death was not previously identified in nature, severity, or degree of incidence in the investigational plan, Investigator's Brochure or protocol, or any other unanticipated serious problem associated with the Test article that relates to the rights, safety and welfare of subjects.

